5.9 Analysis of Site-Reported Serious and Non-Serious Adverse Events

Subject-level event rates will be calculated at various time points (e.g. exact days) based on all events reported by the site regardless of whether or not they are ultimately adjudicated. These safety parameters will be summarized using descriptive statistics.

5.10 Scoring Systems of Target Lesion for HCC

There is a few scoring systems to measure a liver function in the study.

5.10.1 ECOG Performance Status

The Eastern Cooperative Oncology Group (ECOG) performance status describes a subject's level of functioning in terms of the ability to self-care, daily activity, and physical ability (e.g. walking, working, etc.).

Score	Description
0	Fully active, able to carry on all pre-disease performance without restriction
1	Restricted in physically strenuous activity but ambulatory and able to carry out work of a light or sedentary nature (e.g. light housework, office work).

2	Ambulatory and capable of all self-care but unable to carry out any work activities. Up and about more than 50% of waking hours.
3	Capable of only limited self-care, confined to bed or chair more than 50% of waking hours.
4	Completely disabled. Cannot carry on any self-care. Totally confined to bed or chair.
5	Dead

5.10.2 Child-Pugh Score

The Child-Pugh score is a measure of liver function based on the following 5 items that tells how well the liver is working.

- Bilirubin levels in the blood
- Albumin levels in the blood
- How quickly the blood clots (prothrombin time)
- If fluid has collected in the abdomen (ascites)
- Brain function (encephalopathy)

Each one is given a number score as follows:

		1 point	2 points	3 points
Serum	mg/dL	<2	2-3	>3
Bilirubin	μmol/L	<34.2	34.2-51.3	>51.3
Serum	g/dL	>3.5	2.8-3.5	<2.8
Albumin	g/L	>35	28-35	<28
INR		<1.7	1.7-2.30	>2.30
Ascites		None	Mild	Severe
Hepatic encephalopathy		None	Grade I-II	Grade III-IV

If there are several test results for one test item, the lower point (the worst case) will result will be used to determine the Child-Pugh class. Based on that score, people fall into 1 of 3 classes:

- Class A (5-6 points): the liver is working normally.
- Class B (7-9 points): the liver is mild to moderate illness and the subject may be offered treatment such as surgery or chemoembolization.
- Class C (10-15 points): there is severe liver damage; unfortunately the outlook is then quite poor. The subject is often too sick to have treatment for the cancer.

Chronic liver disease is classified into Child-Pugh class A to C. The one-year and two-year survival rates are based on meta-analysis (Cholongitas, E. et al, 2005, Alimentary Pharmacology

and Therapeutics). The category may be classified further such as "B7" representing Child-Pugh class B with a score of 7. The interpretation for Child-Pugh scores are shown below:

Point	Class	One year survival	Two year survival
5-6	A	100%	85%
7-9	В	81%	57%
10-15	С	45%	35%

5.10.3 mRECIST Criteria

The mRECIST response assessment of target lesion for HCC is to measure on MRI in HCC subjects treated with chemoembolization to predict long-term survival. The EASL criteria describes below:

Response Category	mRECIST Criteria
Complete Response (CR)	Disappearance of any intratumoral arterial enhancement in all target lesions
Partial Response (PR)	At least a 30% decrease in the sum of the diameters of viable (enhancement in the arterial phase) target lesions, taking as reference the baseline sum of the diameters of target lesions.
Stable Disease (SD)	Any cases that do not qualify for either PR or PD
Disease Progression (PD)	An increase of at least 20% in the sum of the diameters of viable (enhancing) target lesions, taking as a reference the smallest sum of the diameters of viable (enhancing) target lesions recorded since treatment started.

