9.2. Inclusion Criteria

Subjects may be enrolled in the study if they meet all of the following criteria:

- 1. Patient is able to provide informed consent and must sign the Institutional Review Board/Ethics Committee (IRB/EC) approved Informed Consent Form.
- 2. Male or female of age \geq 18 and \leq 75 years.
- 3. Confirmed diagnosis of HCC according to the diagnostic criteria included in the management guideline issued by China's Ministry of Health in 2017.
- 4. HCC is diagnosed for the first time or recurrence of tumor after surgical or ablation treatment
- 5. Single tumor less than 7cm in diameter or multiple tumors with less than 3 lesions with >1cm in diameter, individual diameter <7cm and less than 10cm in total diameter.
- 6. No previous chemotherapy, radiotherapy or transarterial embolization (with or without chemotherapy) for HCC
- 7. Preserved liver function (Child-Pugh A or B7).
- 8. ECOG Performance Status 0 or 1.

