Appendix C: Child-Pugh Score

		1 point	2 points	3 points
Serum	mg/dL	<2	2-3	>3
Bilirubin	μmol/L	<34.2	34.2-51.3	>51.3
Serum	g/dL	>3.5	2.8-3.5	<2.8
Albumin	g/L	>35	28-35	<28
INR		<1.7	1.7-2.30	>2.30
Ascites		None	Mild	Severe
Hepatic encephalopathy		None	Grade I-II	Grade III-IV

Class A: 5-6 points, Class B: 7-9 points, Class C: 10-15 points

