4.4 Baseline Data Analyses

Baseline demographics, procedure and assessments will be summarized for the study. For continuous and/or ordinal variables, the descriptive statistics will include mean, standard deviation, number evaluated, minimum and maximum. Some specific variables may also include additional statistics such as median and confidence intervals. For binary or categorical variables,

the descriptive statistics will include percentage, numerator, denominator, and number evaluated. Some variables may include confidence intervals as needed.

The following assessments will be performed during the follow up visits as well as the baseline visit and change from baseline analysis may be performed on clinically meaningful variables.

- Physical examination
- Child-Pugh score
- ECG
- Laboratory tests
- Imaging and tumor measurement
- ECOG performance status
- Concomitant medication

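### SAP 5.10.2 contradicts itself on repeat Child-Pugh results: it calls the lower point the worst case, but on its own scale the lower point is the best case

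*SAP*

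**What the plan says.** SAP 5.10.2 scores five items (bilirubin, albumin, INR, ascites, encephalopathy) at 1, 2 or 3 points each and adds them. Its rule for assigning the class when an item has repeat results reads, in its main part: "If there are several test results for one test item, the lower point (the worst case) will result will be used to determine".

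The same section explains the totals. At the bottom of the range: "Class A (5-6 points): the liver is working normally". In the middle: "Class B (7-9 points): the liver is mild to moderate illness". At the top: "Class C (10-15 points): there is severe liver damage; unfortunately the outlook is then quite poor". Protocol Appendix C has the same item table and the same bands ("Class A: 5-6 points, Class B: 7-9 points, Class C: 10-15 points") but no rule for repeat results.

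The score is used in two places. Protocol 9.2 limits entry to class A or B7, that is, a total of 5 to 7. SAP 4.4 lists Child-Pugh among the assessments made at baseline and follow-up, and says that "change from baseline analysis may be performed on clinically meaningful variables". SAP 5.11, 6 and 7 give all programming and validation to an independent CRO.

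**The concern.** The instruction and its parenthesis point in opposite directions. If fewer points mean better liver function, choosing the lower point chooses the better result, yet the sentence describes that choice as the worst case. A programmer has to follow one half and ignore the other. Two programmers working independently could differ, or both could code the minimum and agree on a best-case score that the SAP did not intend.

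What is at stake is the derived Child-Pugh score and class. A best-case rule would make liver function look somewhat better in the baseline description and in the follow-up summaries, for those subjects whose repeat results disagree.

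**Working it through.** **1. Direction of the scale.** Five items at 1 to 3 points give totals from 5 × 1 = 5 to 5 × 3 = 15. This reproduces the bands in SAP 5.10.2 and Protocol Appendix C: A = 5–6, B = 7–9, C = 10–15. On every item 1 point goes to the most favourable finding (bilirubin <2 mg/dL, albumin >3.5 g/dL, INR <1.7, no ascites, no encephalopathy) and 3 points to the least favourable. The SAP's survival table runs the same way, with one-year survival of 100%, 81% and 45% for A, B and C. So for all five items a lower point is a better result.

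**2. Could *lower* mean the lower laboratory value?** Scored with the SAP table, using assumed values:

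| Item | Lower value | Higher value | Lower value is |
|---|---|---|---|
| Albumin, g/dL | 3.2 → 2 points | 3.6 → 1 point | worse |
| Bilirubin, mg/dL | 1.8 → 1 point | 2.5 → 2 points | better |
| INR | 1.5 → 1 point | 1.8 → 2 points | better |

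This reading gives the worst case for albumin only, and it has no meaning for ascites or encephalopathy. It does not rescue the sentence.

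**3. When the two codings differ.** For each item, the literal coding takes the minimum of the points and the coding from the parenthesis takes the maximum. They are equal when all repeat results lie in one band. They differ by 1 point for an item whose results straddle one cut-off, and by 2 points if the results span both cut-offs.

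**4. Illustration.** These are assumed follow-up values, not trial data: bilirubin 1.8 and 2.0 mg/dL (1 and 2 points), albumin 3.6 and 3.2 g/dL (1 and 2 points), INR 1.5, no ascites, no encephalopathy (1 point each).

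- Lower points: 1 + 1 + 1 + 1 + 1 = 5, class A.
- Higher points: 2 + 2 + 1 + 1 + 1 = 7, class B (B7).

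The same results with mild ascites (2 points) add 1 to each total:

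- Lower points: 6, class A.
- Higher points: 8, class B (B8).

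One item can be enough. With bilirubin fixed at 1.8, albumin 3.6 and 3.2, INR 1.5, mild ascites and no encephalopathy:

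- Lower points: 1 + 1 + 1 + 2 + 1 = 6, class A.
- Higher points: 1 + 2 + 1 + 2 + 1 = 7, class B.

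**5. What depends on the score.** The only hypothesis test is 6-month ORR (SAP 2 and 3.1), which is judged on imaging criteria. Child-Pugh is not among the secondary endpoints in SAP 5.1. The sample size inputs in SAP 3.1.3 (45%, 60%, one-sided 2.5%, power of 85%, 10% attrition) do not involve it.

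**The case against.** The best case on the other side is that the intent is stated in the sentence itself. The wording is visibly garbled, the parenthesis names the worst case, and a careful programmer would probably code the maximum. That stands as a limit. The documents do not show that repeat results would in fact be scored at their best, only that the rule permits it if read literally. It does not remove the contradiction, because the operative word is still the wrong one and no other section corrects it.

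Stronger consequences are tempting, and the documents do not support them:

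- *The rule lets ineligible subjects in.* Eligibility is decided before treatment under Protocol 9.2, 9.3 and 10.1, and the protocol has no repeat-result rule. The sentence appears only in the SAP, as an analysis derivation. It could affect a later check against A/B7, but not the enrolment decision. At baseline, moreover, exclusion criterion 5 removes bilirubin above 2 mg/dL, so an eligible subject can score 2 points on bilirubin only at exactly 2 mg/dL.
- *Every repeat-tested score is biased.* Only results that straddle a cut-off change a score. Protocol Table 11.1 plans one laboratory set and one Child-Pugh assessment per visit. Repeats are plausible, since Protocol 11.4 accepts certain recent results and visit windows are ±14 days, but no frequency is given.
- *Post-treatment decompensation would be hidden.* Death and liver failure are monitored separately (SAP 3.2 and 5.8), and all reported adverse events are summarised. The Child-Pugh change from baseline is optional.
- *The error is worth 100% against 81% one-year survival.* Those figures are background literature on chronic liver disease, and no planned analysis applies them to trial subjects.
- *A subgroup of the primary endpoint is affected.* SAP 5.3 uses the label B7 but presents the split as BCLC stage. The documents do not say that it is derived from this score, and the subgroup summaries are observational in any case.

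**Conclusion.** The rule is wrong as written. On the SAP's own scale the lower point is the best case, so the derivation is ambiguous, and literal coding reverses the stated intent. In the illustrations a subject moves by 1 or 2 points and from class B to class A. The total effect in the trial cannot be estimated, because neither the number of repeat tests nor the share that straddle a cut-off is given.

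The reach is limited to derived Child-Pugh scores and classes at baseline and follow-up, any change from baseline, and any retrospective check against A/B7. It does not affect enrolment decisions, the 6-month ORR test, sample size, alpha or power. It should be corrected because it is an instruction to be programmed and the correction costs almost nothing; it is no threat to the trial's conclusion. The conclusion rests on the SAP's own item table and bands. The laboratory values in the examples are assumed.

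**What to change.** Replace the sentence in SAP 5.10.2 with: *Where an item has more than one result at a visit, the result carrying the higher point (the worst case) determines the Child-Pugh score and class; this applies at baseline and at every follow-up visit.* This keeps the intent that the SAP already states. It also limits the rule to results from the same visit, which the present sentence does not do.

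The cost is one changed word, a short clarification and one line of code (maximum instead of minimum points per item), documented as a SAP amendment before the analysis, as SAP 5.12 provides. The downside is that some Child-Pugh summaries may look slightly less favourable than under literal coding.

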5.10.4 EASL Criteria

The EASL response assessment of target lesion for HCC is to measure on MRI in HCC subjects treated with chemoembolization to predict long-term survival. The EASL criteria describes below:

Response Category	EASL Criteria
Complete Response (CR)	Disappearance of all known disease and no new lesions determined by two observations not less than 4 weeks apart
Partial Response (PR)	At least 50% reduction in total tumor load of all measurable lesions determined by two observations not less than 4 weeks apart
Stable Disease (SD)	Any cases that do not qualify for either PR or PD

Disease Progression (PD)	At least 25% increase in size of one or more measurable lesions
	or the appearance of new lesions
	of the appearance of new resions

5.11 Analyses Software

All statistical analyses will be performed and validated by the independent CRO (e.g. IQVia in Bangalore) using the Statistical Analysis Software (SAS), version 9.2 or later (Copyright © 2002-2010 by SAS Institute Inc., Cary, North Carolina 27513, USA. All rights reserved). BSC will review statistical reports.

5.12 Changes to Planned Analyses

Any changes to the planned statistical analyses made prior to performing the primary endpoint analysis will be documented in an amended Statistical Analysis Plan approved prior to performing the analysis. Changes from the planned statistical methods after performing the analysis will be documented in the clinical study report along with a reason for the deviation.

6 VALIDATION

All clinical data reports generated per this plan will be validated per 90702587, Global WI: Clinical Data Reporting Validation. Statistical analyses and validation will be done by an independent CRO.

7 PROGRAMMING CONSIDERATIONS

All statistical programming tasks will be performed by the independent CRO.

7.1 Derivation of Variables

- The number of subjects included in the event rates (overall and individual components) will be based on subjects who have adequate follow-up and/or have experienced any component of events within the analysis interval.
- The last follow-up date will be the latest of the following dates for each subject: onset date of an event, DEB-TACE dates, treatment evaluation follow-up dates, end of study date, end of treatment date, and follow-up visit dates.
- Days to event (or last known status) = event (or status) date index procedure date (e.g. DEB TACE1).

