11.10. Study Completion

All subjects who completed the 12 months follow-up, or withdrawn (due to death or loss to follow-up), or will be treated as study termination. Any adverse events occurred afterwards will be addressed by the physician per standard treatment.

Subjects may withdraw their consent and discontinue participation in the clinical study at any time, for any reason, without prejudice to further treatment. If a subject no longer wants to receive study treatment, but is willing to come for follow-up appointments, the subject's request should be honored, if possible.

If for any reason a subject is withdrawn or terminated before completing the study, the reasons for withdrawal or termination must be documented.

If a subject discontinues treatment due to an adverse event or clinical laboratory abnormality, the subject should be followed-up until the event resolves or the subject stabilized.

12. Statistical Considerations

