5.7.1 Kaplan-Meier for OS

OS is defined as the length of time from the treatment initiation, that treated subjects are still alive. The Kaplan-Meier analysis is aimed to capture the all-cause death for each subject. Subjects who are lost-to-follow will be considered being censored.

There are three critical data items to be captured:

- Death date
- The very last date in the database (e.g. follow-up visit date and/or site reported AE date)
- The desired cut-off days (e.g. 6-month OS at 182 days, 12-month OS at 365 days)

In addition to the Kaplan-Meier survival curve, the median survival time (mOS) will also be used to represent the study cohort.

5.7.2 Kaplan-Meier for TTP

TTP is defined as the length of time from the treatment initiation to either the date of the first disease progression occurred, as assessed by the investigators, or the date of the subject died due to any cause, whichever comes earlier.

TTP (also referred as "time to treatment failure") will be measured by a few data items list below:

- The date of the disease progression in the Overall Response form
- The date of lost-to-follow due to:
 - o Adverse events
 - o Progressive disease/insufficient therapeutic response
 - Death
 - o Failure to return
 - o Refusing treatment/being unwilling to cooperate/withdrawing consent
- The very last date by scanning all available dates in the database
- The desired cut-off days

In addition to the Kaplan-Meier estimates, the median will also be used to represent the study cohort.

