5.7.3 Kaplan-Meier for EHS

The time to EHS is defined as the length of time from the treatment initiation to the development of extrahepatic spread of the disease via imaging assessment.

The data items to be considered will include:

- The date of the extrahepatic spread in the Overall Response form
- The very last date by scanning all available dates in the database
- The desired cut-off days

5.7.4 Kaplan-Meier for PPF

PPF is defined as the length of time from the treatment initiation, that treated subjects are still progression-free.

The data items to be captured will include:

- The date of the disease progression in the Overall Response form
- The very last date by scanning all available dates in the database
- The desired cut-off days

The proportion of any time point will be determined by the Kaplan-Meier estimates.

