5.8.1 Event Rates Presented Using "Month" System

The denominator will be based on number of subjects who reach the protocol-defined lower window (i.e. adequate follow-up days) and/or subjects who experience the event. The numerator will be based on number of subjects-level events within the protocol-defined upper window. Subject-level events beyond the upper window will be counted as next visit.

Follow-up Visit	Protocol Defined Lower Window	Protocol Defined Upper Window
1 Month	16	44
3 Months	77	105
6 Months	169	197
12 Months	351	379

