5.8.2 Event Rates Presented Using Exact Days Cut-Off System

The denominator will be based on number of subjects who reach the protocol-defined lower window (i.e. adequate follow-up days) and/or subjects who experience the event. The numerator will be based on number of subjects-level events within the exact desired cut-off days. Subject-level events beyond the exact cut-off days will be counted as next cut-off days.

Follow-Up Cut-Off	Days for Adequate Follow-Up	Maximum Days to Event
30 Days	16	30
91 Days	77	91

Follow-Up Cut-Off	Days for Adequate Follow-Up	Maximum Days to Event
183 Days	169	183
365 Days	351	365

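### SAP 7.1 lets an undefined end-of-study date set a lost subject's last follow-up, which can raise one-year survival and lower 6- and 12-month event rates

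*SAP*

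**What the plan says.** SAP 7.1 gives the rule: "The last follow-up date will be the latest of the following dates for each subject". The dates are "onset date of an event, DEB-TACE dates, treatment evaluation follow-up dates, end of study date, end of treatment date, and follow-up visit dates". No item is restricted to subjects who completed the study.

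Three other places bear on it:

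- **SAP 5.7.1 (OS).** "Subjects who are lost-to-follow will be considered being censored", but that sentence names no censoring date. The data item is "The very last date in the database (e.g. follow-up visit date and/or site reported AE date"), and both examples are dates on which someone had information about the subject.
- **SAP 5.7.2 to 5.7.4 (progression and extrahepatic spread).** Each lists "The very last date by scanning all available dates in the database", with no restriction on the kind of date.
- **SAP 5.8.1 and 5.8.2 (binary event rates).** "The denominator will be based on number of subjects who reach the protocol-defined lower window (i.e. adequate follow-up days") or who have the event. The lower windows are days 16, 77, 169 and 351.

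On study exit, Protocol 11.10 says: "All subjects who completed the 12 months follow-up, or withdrawn (due to death or loss to follow-up), or will be treated as study termination". It sets no time limit for declaring a subject lost and no rule for dating that exit. Vital status is a listed item at the 6- and 12-month visits (Protocol 11.8 and 11.9). No vital-status check is described for subjects lost before those visits.

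**The concern.** Because 7.1 takes a maximum, and visits, evaluations, treatment sessions and event onsets are already on the list, the end-of-study date changes a result only when it is later than all of them. Apart from a death or a contact outside a visit, that is time in which nobody observed the subject.

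Take a subject last seen on day 91 whose end-of-study date is entered as day 370. Under 7.1 this subject is at risk and alive through day 365, and has adequate follow-up without an event at both 6 and 12 months (370 exceeds 169 and 351). A death on day 200 that the site never learned of would be invisible in both analyses.

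At stake are one-year OS, which is a named secondary endpoint, and the site-reported adverse event rates that SAP 5.9 presents at several time points.

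**Working it through.** **Design figures.** The documents state no expected one-year OS for this trial and no 12-month loss. The one-year survival table in SAP 5.10.2 (100% for Child-Pugh A, 81% for B) describes chronic liver disease and is not a design assumption. The only design figure is the sample size, which reproduces:

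- n = [(1.960 × √(0.45 × 0.55) + 1.036 × √(0.60 × 0.40)) / 0.15]² = 97.7, so 98, with power 85.1%.
- 98 / 0.9 = 108.9, so 109.

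The last follow-up date enters none of this. SAP 3.1.1 drops subjects without a 6-month assessment from the response rate.

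**Direction.** Moving a censored subject's last date later leaves the observed deaths unchanged and enlarges later risk sets. Each Kaplan-Meier factor 1 − d/n then stays the same or rises. Adding event-free subjects to a denominator can only lower a proportion.

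**Size: inputs.** N = 109 (Protocol 12.1.1.2). Assumed: constant hazard; true one-year OS of 95%, 85% or 70%; 5%, 10% or 20% lost, unrelated to risk; last contact uniform between day 30 and day 183. The documents' only loss figure is 10% by 6 months.

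**OS by formula.** If every lost subject's end-of-study date is at or after day 365, silent deaths are scored as survivors:

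excess OS = loss × [S(last contact) − S(365)], with S(t) = S(365)^(t/365).

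At the mean last contact, day 106.5 (106.5/365 = 0.292):

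- 95%: S = 0.985. 10% × (0.985 − 0.950) = 0.35 points.
- 85%: S = 0.954. 10% × (0.954 − 0.850) = 1.0 point.
- 70%: S = 0.901. 10% × (0.901 − 0.700) = 2.0 points, or 4.0 points at 20% loss.
- 70%, 20% loss, all last seen on day 30: S = 0.971. 20% × (0.971 − 0.700) = 5.4 points.

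**OS by simulation** (2,000 runs per scenario, Kaplan-Meier at day 365):

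| True OS | Loss | Last-contact date | End-of-study date at or after day 365 | End-of-study date 60 days after contact |
|---|---|---|---|---|
| 95% | 10% | 95.0% | 95.4% | 95.2% |
| 85% | 10% | 85.1% | 86.1% | 85.2% |
| 70% | 10% | 70.1% | 72.1% | 70.6% |
| 95% | 20% | 95.0% | 95.7% | 95.2% |
| 85% | 20% | 85.0% | 87.1% | 85.5% |
| 70% | 20% | 69.9% | 74.0% | 70.9% |

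At 5% loss the day-365 column reads 95.1%, 85.5% and 71.1%. With no lag (85%, 10% loss) both methods give 85.1%.

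**Binary rate at 12 months, true 15%, 10% loss.** Observed events are 15% − 1.04% = 13.96% of subjects.

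- End-of-study denominator (everyone counts): 13.96%; simulated 13.9%.
- Last-contact denominator: 1 − 0.10 × 0.954 = 0.905, and 0.1396 / 0.905 = 15.4%; simulated 15.4%.

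**If loss is related to risk.** With lost subjects dying at twice the rate after loss (10% lost, true OS 84.1%), last-contact censoring reads 85.0% and the end-of-study date 86.1%. Both are too high, the second more so.

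**The case against.** The strongest objection is that the harmful premise is not in the documents. A reader might infer that the end-of-study date is an administrative close-out date taken from an exit form, and hence that OS will be overstated. The SAP says only that such a date exists. If sites enter the last contact date, nothing is wrong. A reader might also take 7.1 to label this date as the last known status. That phrase stands in a separate bullet on computing days to event and, if anything, suggests that status should be known. The contact-type examples in 5.7.1 point the same way, and no text expressly ties the 7.1 date to OS censoring. All of this stands, and it makes the bias conditional. It does not remove the rule: 7.1 names the date, takes the maximum, and nothing elsewhere blocks it.

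Second, the effect is modest. At 85% OS and N = 109 the standard error is √(0.85 × 0.15 / 109) = 3.4 points, so the 95% interval is about ±6.7 points. A shift of 1 point lies well inside it, and OS carries no hypothesis (SAP 5.1). That stands. Unlike sampling error, however, the shift has a known direction and costs almost nothing to remove.

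Third, 20% loss is an assumption. Protocol 10.3 plans for at most 10% attrition for all reasons at 6 months. It is shown here because no 12-month figure is given.

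Fourth, a reader might think that the safety triggers are diluted. The three named events are watched over 6 weeks (SAP 3.2) and used only for monitoring (SAP 5.8), so only subjects lost very early could matter.

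**Conclusion.** The point holds as a conditional risk that the SAP should close. The 7.1 rule permits unobserved time to count as alive and event-free. Where it does, one-year OS can only be biased up and the 6- and 12-month event rates down.

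If all lost subjects have end-of-study dates at or after day 365, the OS excess at 10% loss is about 0.4 to 1 point for a true OS of 95% to 85%, and about 2 points at 70%. It reaches about 4 to 5 points at 20% loss and 70% OS. A 60-day lag gives at most about 1 point, and no lag gives none. A true 15% event rate at 12 months reads about 13.9% at 10% loss. These figures assume constant hazard, non-informative loss, and OS and loss values that the documents do not supply.

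The documents do not support a claim that OS is overstated as planned, or that the trial's conclusion is at risk. The 6-month response rate, its test and the sample size are unaffected, and the 6-week safety triggers largely so.

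**What to change.** In SAP 7.1, count the end-of-study date only when it is the date of a completed visit, a documented contact or a death. For all other lost or withdrawn subjects, use the last date the subject was known to be alive. State that this date governs OS censoring (5.7.1) and adequate follow-up (5.8.1 and 5.8.2). Align the open wording on database dates in 5.7.2 to 5.7.4 so that it too excludes an end-of-study date without contact.

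The cost is one sentence plus alignment and a small programming change. SAP 5.12 allows it by amendment before the primary analysis. Twelve-month denominators become slightly smaller, and OS may read slightly less favourably. The binary rates then err slightly upward, because lost subjects with events stay in while event-free lost subjects drop out (about 15.4% for a true 15%). Reporting a Kaplan-Meier estimate beside each binary rate would make that visible.
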